The **central hypothesis** of this project is that mirtazapine will improve anxiety when administered to children and adolescents with PDD. We also hypothesize that mirtazapine will be safe and well tolerated. This study will provide much needed pilot data regarding efficacy and tolerability of mirtazapine for these symptoms in autism and is a necessary first step prior to conducting a larger, more definitive randomized controlled trial.

We plan to test the central hypothesis and accomplish the objectives of this application by pursuing the following **specific aims**:

1. **Determine whether mirtazapine shows evidence of efficacy, safety, and tolerability in children and adolescents with PDD.** This aim addresses our central hypothesis that mirtazapine will be efficacious and safe in the treatment of anxiety in children and adolescents with PDD.
2. **Determine the effects of placebo on anxiety symptoms in children with PDD.** This will be an important aim prior to conducting a more definitive trial since the magnitude of placebo effect for this specific symptom in PDD is unknown.

- 3. Determine which semi-structured interviews and existing anxiety rating scales would be most useful for characterizing participants and assessing anxiety treatment effects.** A variety of outcome measures of anxiety will be used to better assess their applicability and feasibility in the PDD population.

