### **Safety Monitoring:**

Adverse events, vital signs, height, and weight will be collected at each clinic visit. A Comprehensive Metabolic Profile and CBC will be collected at baseline and endpoint. Standard methods and precautions will be used to protect the venipuncture site from bleeding and infection. In addition, a trained pediatric phlebotomist will perform all venipunctures that are required. A research assistant, who will be familiar with the subjects, will accompany the subject and their parents for the venipuncture. Parents are encouraged to remain with the subject at all times. To minimize the subject's anxiety and phobic reactions, we "talk through" the procedure with the subject so that they might know, to some extent, what to expect. For subjects who are minimally verbal, we use visual supports in order to prepare the participants for the blood draw. Topical anesthetics (e.g., EMLA or lidocaine cream) are sometimes used as well at the discretion of the nurse or investigator.

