Adverse events will be collected via a structured side effect rating scale completed with the participant and their primary caregiver. This will include a list of side-effects that have been reported with mirtazapine at a rate greater than 1% including sedation, sleep disturbance, dry mouth, increased appetite, nausea/vomiting, constipation, dyspnea, urinary frequency, back pain, edema, myalgia, dizziness, weakness, tremor, irritability, abnormal dreams, abnormal thinking, and confusion. Weight gain is a potential side effect especially in those subjects that have been on atypical antipsychotic medications which can also cause weight gain. Parents of the subject will be informed of this risk in the informed consent prior to participation in the study. Each of these side-effects plus any additional complaints will be rated at baseline on a 4-point scale by the caregiver as follows: 0 = none; 1 = mild; 2 = moderate; 3 = severe. This scale is similar to that used by the RUPP Autism Network (Aman et al., 2005). Suicidality will be assessed at each visit by directly asking the subject (when verbal skills are sufficient) and caregiver about any thoughts or behaviors that directly or indirectly might indicate suicidality (e.g., morbid thoughts, self-injury, statements about life not being worth living), when indicated by positive responses. At baseline, the Columbia-Suicide Severity Rating Scale (C-SSRS) will be administered per the instructions at [www.cssrs.columbia.edu/clinical\\_trials.html](http://www.cssrs.columbia.edu/clinical_trials.html). The C-

SSRS will also be administered at each subsequent visit following the first report of suicidality. Subjects and caregivers will also have information on how to contact the on-call physician from our practice group who provides coverage 24 hours/day and 365 days/year. Physicians taking call are familiar with research protocols and can contact the principal investigator at any time.

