All adverse events picked up on the rating scale as new will be recorded by the physician. The physician will also ask about any visits to the doctor, new medication use (e.g., OTC cold medicine), or any other complaints, in order to be confident that most AEs are uncovered. The physician will keep a running log of adverse events that will record the date of onset, date of resolution, seriousness, severity, and relationship to study intervention (e.g., definite, probable, possible, remote, or none) as well as whether the adverse event led to a change in study intervention or other treatment.

A physician will review vital signs and laboratory data, as they become available. All significant AEs as well as the progress of the study will be reviewed and discussed in detail at the biannual meetings of the **Lurie Center Data and Safety Monitoring Board (DSMB)**. Special attention will be made by the treating physician to note all weight gain trends and bring any concerns to the DSMB. The DSMB is currently being formulated for the Lurie Center and will include rotating members of the Lurie Center including pediatricians, pediatric and adult neurologists, child and adolescent psychiatrists and independent members outside the Lurie Center.

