#### **Statistical Analysis Plan:**

Since this is a preliminary trial that is not powered to show that mirtazapine is better than placebo in the treatment of anxiety in children and adolescents with PDD, we will analyze the data to determine whether the following pre-specified positive indicators of efficacy are present.

1. Significant improvement in PARS score with mirtazapine.
2. Proportion of subjects receiving mirtazapine rated as responders is 50% or greater.
3. Change in PARS score is numerically greater with mirtazapine than placebo.
4. Proportion of subjects rated as responders to mirtazapine is numerically greater than placebo.

Outcome measures will also be analyzed to determine whether there are statistically significant differences between mirtazapine and placebo. However, these will be considered exploratory since they may be underpowered.

The primary outcome measure, PARS score, and other continuous measures will be analyzed using a mixed effects linear model using PROC MIXED in SAS with a REPEATED statement. Prior to running analyses, each dependent variable will be checked for normality and transformed if necessary. In accordance with intention-to-treat principles, data from all subjects having at least one visit following baseline will be analyzed. Significant main effects will need to be significant at an alpha level of 0.05.

For the CGI-I rating, subjects classified as “much” or “very much improved” will be defined as **responders** and all other classifications will be regarded as non-responders. We will be using this classification of the subjects throughout the trial as the dependent variable in these analyses. Hence, the CGI-I dichotomous variable will be examined over the study using a model with time treated as a repeated factor and treatment group as a fixed effect.

The occurrence of particular adverse effects during the 10-week treatment period will be compared between groups using Chi-square tests. In addition to absolute measures, height, weight and body mass index will be transformed to standardized z scores using anthropometric indices based on the 2000 Centers for Disease Control and Prevention age- and gender-normed growth charts (<http://www.cdc.gov/growthcharts/>). These z scores will then be analyzed in a similar manner to those used for other continuous measures described above.

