### **Sample Size Consideration and Power Analysis:**

The baseline to endpoint comparisons of mirtazapine (n=20) have 80% power to detect an effect size of 0.7 (two-tailed significance of 0.05). The mirtazapine (n=20) vs. placebo (n=10) analyses of the secondary comparisons have 80% power to detect an effect size of 1.1.

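### Listed side-effects carry a severity grade, but their only planned comparison between arms is occurrence yes/no, so a mild and a severe effect count the same

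*Combined protocol and SAP*

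**What the plan says.** Aim 1 (A. Specific Aims) is to "Determine whether mirtazapine shows evidence of efficacy, safety, and tolerability in children and adolescents with PDD".

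Under Safety Monitoring, "Adverse events, vital signs, height, and weight will be collected at each clinic visit", using a structured side-effect scale completed with the child and caregiver. It lists 18 effects, among them sedation, sleep disturbance, increased appetite and irritability. Each is "rated at baseline on a 4-point scale by the caregiver as follows: 0 = none; 1 = mild; 2 = moderate; 3 = severe". The physician logs whatever the scale shows as new, and the log is to "record the date of onset, date of resolution, seriousness, severity, and relationship to study intervention". The log's severity levels are not defined.

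The Statistical Analysis Plan gives one sentence to these effects: "The occurrence of particular adverse effects during the 10-week treatment period will be compared between groups using Chi-square tests". It does not say whether the chi-square is continuity-corrected or replaced by an exact test. Height, weight and BMI are converted to z scores and analysed like the other continuous measures.

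**The concern.** The planned comparison cuts an ordinal measure at none versus any, and the plan gives no reason for the cut. A child with one mild complaint and a child with a severe one enter the result identically.

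This matters because tolerability is part of aim 1 and the trial is meant to prepare a larger one. The sponsor's own Preliminary Studies section summarises side-effects by how severe they were, calling them mostly transient or mild. The present plan has no between-arm output that could support or contradict that description under placebo control. If a symptom is reported at some time by most children in both arms, the occurrence count can be level while severity differs.

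There is also a data problem. The sentence defining the 0-3 grade says it is applied at baseline. Repetition at later visits is implied, because the log depends on the scale showing something as new, but it is not stated. Grades that are not recorded on treatment cannot be recovered afterwards.

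**Working it through.** **Inputs.** Arm sizes of 20 and 10 come from the Sample Size section. Two-sided 0.05 is stated there for the baseline-to-endpoint comparison and is assumed here for the side-effect tests. The documents give no side-effect rates or severity distributions for either arm, so every rate below is an assumption.

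**The plan's own figure.** The only between-arm power statement is "The mirtazapine (n=20) vs. placebo (n=10) analyses of the secondary comparisons have 80% power to detect an effect size of 1.1". Non-centrality = 1.1 × √(20 × 10 / 30) = 2.84. Normal approximation: Φ(2.84 − 1.96) = 81.1%. Noncentral t on 28 df: 78.3%. The stated 80% is reproduced. It is a detectable effect for the secondary comparisons, and says nothing about expected side-effects.

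**What occurrence cannot see.** Suppose 80% of both arms report an effect. Among those affected, the mild/moderate/severe split is 20/40/40 on mirtazapine and 80/15/5 on placebo. Expected counts:
- Mirtazapine: 20 × 0.8 = 16 affected, of whom 3.2 are mild, 6.4 moderate and 6.4 severe.
- Placebo: 10 × 0.8 = 8 affected, of whom 6.4 are mild, 1.2 moderate and 0.4 severe.

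The planned test compares 16/20 with 8/10, a difference of zero.

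**Power under assumed rates.** The uncorrected Pearson chi-square on occurrence was computed by exact enumeration of the two binomials. The tie-corrected Wilcoxon test on worst grade was simulated. Under no effect the Wilcoxon test rejected in 4.6-4.9% of trials and the chi-square in 4.7-5.2%, so the two are comparable.

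| Assumed pattern (mirtazapine vs placebo) | Chi-square | Wilcoxon | Change, points |
|---|---|---|---|
| 80% vs 80%; 20/40/40 vs 80/15/5 | 3.7% | 47.8% | +44 |
| 80% vs 50%; 40/40/20 vs 70/25/5 | 40.8% | 54.1% | +13 |
| 70% vs 40%; 40/40/20 vs 70/25/5 | 36.6% | 46.2% | +10 |
| 60% vs 30%; 40/40/20 vs 70/25/5 | 35.2% | 41.1% | +6 |
| 80% vs 50%; proportional odds | 40.8% | 46.9% | +6 |
| 70% vs 40%; proportional odds | 36.6% | 38.0% | +1 |
| 70% vs 40%; same mix in both arms | 36.6% | about 30% | about −7 |
| 30% vs 10%; 40/40/20 vs 70/25/5 | 15.7% | 17.0% | +1 |
| 20% vs 5%; 40/40/20 vs 70/25/5 | 5.4% | 5.6% | 0 |

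The largest loss among the same-mix patterns was 21 points, at the high end of the rates tried. For example, 90% vs 50% with a 40/40/20 split in both arms goes from 68.1% to about 47%.

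**Choice of comparator.** At 70% vs 40%, chi-square power is 36.6% uncorrected, 24.2% with Yates' correction and 27.6% by Fisher's test. The table uses the most powerful of the three, so its gains do not come from a weak comparator.

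**Role of baseline.** If occurrence means a grade above baseline, the fair comparator is the chi-square on such emergent effects. Simulations with a latent severity shift and an assumed baseline-to-follow-up correlation gave these changes for a Wilcoxon test on raw worst grade:
- correlation 0.5: +2 to +17 points
- correlation 0.7: −6 to +1 points
- correlation 0.85: −9 to −22 points

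A Wilcoxon test on change in grade from baseline was about 3 to 11 points above the emergent-effect chi-square in latent-shift runs.

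**A different cut does not help in general.** Testing moderate-or-severe yes/no, at 70% vs 40% with 40/40/20 vs 70/25/5, gives 36.0% against 36.6% for occurrence.

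**The case against.** A reader might infer that the yes/no cut costs a definite amount of power, say 5 to 25 points for common effects. A latent shift does give figures of that kind: at 50% placebo occurrence and a 1.1 SD shift, 57.9% against 71.6%. But such a shift forces effects to become more frequent and more severe together, which favours the severity test. The documents supply neither the rates nor the shift, and their only drug-specific evidence is that earlier side-effects were mostly mild. With an unchanged severity mix the sign reverses. This objection stands, and no single power loss can be claimed.

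Nor is background symptomatology sure to fill the placebo count. The log records what is new relative to a graded baseline, so occurrence can be read as emergent. That also stands, and it means raw worst grade would be the wrong severity measure: a child with unchanged severe irritability would score 3. It does not rescue the plan, because emergent occurrence still ignores severity and a rule based on newness may leave out a pre-existing symptom that worsens.

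A reader might also infer that tolerability as a whole is dichotomised, or that these tests decide whether a larger trial follows. Neither is supported. Weight and BMI stay continuous, significant events go to the data and safety monitoring board, and the four pre-specified indicators all concern efficacy.

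Finally, a severity test for each of 18 listed effects adds unadjusted tests: at nominal size, 18 × 0.05 = 0.9 expected false positives if nothing differs. This is a real cost, and a reason to label the tests exploratory and put the weight on the table.

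**Conclusion.** The point holds as one about information and interpretation. Severity is to be recorded, no planned analysis or table compares it between arms, and the tolerability part of aim 1 therefore cannot separate mild from severe effects. A drug effect acting mainly on severity would be missed.

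The consequence for power cannot be fixed from the documents. Under the assumed patterns it runs from a loss of about 20 points (more frequent, same mix) to a gain of 40 or more (same occurrence, very different severity). It is near zero for rare effects. Power is modest for either test under most of these patterns, so the severity comparison belongs beside occurrence and should not replace it. The change is worth making because it is cheap and because ungraded visits cannot be repaired later.

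**What to change.** 1. In Safety Monitoring, state that the same 0-3 caregiver grade is recorded for every listed effect at baseline and at each follow-up visit.
2. In the Statistical Analysis Plan, define an emergent effect as one that is new or graded worse than at baseline. Keep the between-arm comparison of emergent occurrence, naming the chi-square variant or an exact test.
3. Add, for each listed effect, a table by arm of the worst post-baseline grade among new or worsened effects.
4. Add an exploratory tie-corrected or exact Wilcoxon rank-sum test on worst post-baseline grade minus baseline grade, stated to be unadjusted for multiplicity.

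The cost is a protocol clarification, a few sentences in the analysis plan, one table and a set of exploratory tests in 30 children. The scale and the visits already exist, so no extra children or visits are needed. If the grade was not going to be repeated on treatment, recording it adds a small amount of caregiver and data-entry time per visit.

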### **Sample Size Consideration and Power Analysis:**

The baseline to endpoint comparisons of mirtazapine (n=20) have 80% power to detect an effect size of 0.7 (two-tailed significance of 0.05). The mirtazapine (n=20) vs. placebo (n=10) analyses of the secondary comparisons have 80% power to detect an effect size of 1.1.

### **Training and Reliability on Instruments:**

Training on clinician-rated instruments consists of observing videotaped interviews conducted by trained interviewers, then interviewing under direct supervision. CGI Reliability will be conducted in a manner similar to that used by our site in the RUPP Autism Network. Our site is fully certified for using the ADI-R for research purposes.

### **Data Management:**

When a participant is enrolled in the study, he or she will be assigned a unique identification number that is used to identify all data associated with that person, including hard copy, biological specimens, and computerized data. Data will be collected on hard-copy forms and then verified by data entry personnel. All of the hard copy research data is kept in locked file cabinets at the Lurie Center. Only the PI and primary research assistants will have access to these files, ensuring security of the hard copy records.

Once data is obtained, the clinician will review the form to make sure that all required items are completed and to clarify any ambiguous notations before giving it to the research assistant responsible for data entry. Several quality control measures are built into our computerized data management. Data entry forms have been designed that correspond to the measures used in this study. These forms are configured so that out-of-range values cannot be entered; data entry prompts appear in the correct order, including skipping questions when appropriate; and entered values cannot be inadvertently overwritten. Immediately after data entry, a series of logic check programs are run automatically, indicating any entered values that appear incorrect and the reason why. Logic check reports will be reconciled with the hardcopy and, if necessary, the clinician. Changes will then be entered, and the logic check programs executed again in order to detect any new errors resulting from the changed values. The process will continue until no further errors are detected by the logic check programs.

### **Project Milestones:**

**Year 1:** The trial will be initiated after obtaining IRB approval, training of all personnel on study procedures, and achieving reliability on screening and outcome measures. Nine subjects will enroll into the protocol.

**Year 2:** Trial enrollment continues. An additional 12 subjects will be enrolled into the protocol.

**Year 3:** Trial enrollment continues. The final 9 subjects will be enrolled into protocol. Data will be analyzed.

### **End of Trial Alternatives:**

At the completion of the 10-week trial, the prescribing physician will break the blind in order to decide on an appropriate next step for the participant. Placebo treated subjects still exhibiting clinically significant anxiety will be entered into a 10-week open-label trial of mirtazapine of similar design to the double-blind trial with the exception that the outcome measures will be more limited in scope and conducted by the physician. This will help to protect the blinded rater from gaining any knowledge that might influence their ratings during the course of the study. This mechanism has been used successfully in studies conducted by the RUPP Autism Network.

**Schedule of Measures:**

Measure	SC	BL	W2	W4	W6	W10
Diagnostic Exam including history and mental status exam	X					
Physical exam, labs	X					X
Urine Pregnancy Test (females of child-bearing potential only)	X					
Vital signs, height, weight, AEs, Con Meds	X	X	X	X	X	X
ADI-R, ADIS-IV, PPVT-4, SB5, Vineland-II	X					
PARS	X	X	X	X	X	X
SCARED, CASI Anxiety, ABC, CSHQ		X	X	X	X	X
CGI-S, DD-CGAS		X				X
CGI-I			X	X	X	X
C-SSRS	X*	X*	X*	X*	X*	X*

\* - C-SSRS will be administered to child and/or parent if any positive suicidal ideation is reported during clinical assessment. Each visit following the first report of suicidal ideation will include the administration of the C-SSRS.

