## **E. RESEARCH STRATEGY**

### **Study Design:**

A 10-week, flexibly-dosed, double-blind trial with 2:1 randomization to either mirtazapine or placebo was chosen as the optimal way of gathering quality preliminary data. Participants will be seen at screen, baseline (randomization), and following 2, 4, 6, and 10 weeks of treatment. The duration of the trial will allow us to adjust the dose of study drug over the first 6 weeks and allow for stable dosing during the final 4 weeks of the trial. Unbalanced randomization was chosen so that the majority of subjects will receive mirtazapine which will allow us to gather more information about the efficacy of mirtazapine in a broader range of subjects. A placebo control group will help us determine placebo effects in the treatment of anxiety in PDD.

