### **Exclusion Criteria:**

1. **Diagnosis of Rett's disorder or childhood integrative disorder.** Subjects with these other PDDs will not be enrolled since these disorders have a different etiology, course, and treatment response.
2. **Diagnosis of OCD, post-traumatic stress disorder, major mood disorder, psychotic disorder, or substance use disorder.** These disorders are exclusionary since the primary treatment of these disorders may require acute psychosocial treatments or other medications that would confound the assessments.
5. **Presence of any past or present medical conditions that would make treatment with mirtazapine unsafe.** This includes allergy to mirtazapine; agranulocytosis/bone marrow suppression; heart, kidney, or liver disease; unstable seizure disorder; and pregnancy (or being sexually active without using acceptable methods to prevent pregnancy).
3. **Use of other antidepressants or benzodiazepines.** Subjects will need to be off medications from these classes for at least 5 elimination half-lives prior to randomization.
6. **Use of other psychotropic medications which are ineffective, poorly tolerated, or sub-optimal in terms of dose.** A board certified child and adolescent psychiatrist will assess any other psychotropic medications being used and determine whether they are effective, tolerated, and optimal in terms of dose. Concurrent use of a psychotropic medication (other than antidepressants or benzodiazepines) will be allowed if the dose has been stable for 60 days and if they meet the above criteria of effectiveness, tolerability, and dose. Medications for concomitant attention-deficit/hyperactivity disorder symptoms (e.g., stimulants), insomnia (e.g., melatonin), and irritability (e.g., atypical antipsychotics) will be allowed if they meet the above criteria. Any medication that is assessed as possibly contributing to the subject's anxiety symptoms will not be allowed.
7. **Use of linezolid (Zyvox).** Subjects will need to refrain from taking linezolid during the study to prevent a potential drug interaction related to the serotonin syndrome. Linezolid taken in conjunction with mirtazapine could increase the risk of increasing serotonin activity to toxic levels, causing what is known as serotonin syndrome. This syndrome is characterized by at least 3 of the following symptoms: agitation, diaphoresis, diarrhea, fever, hyper-reflexia, incoordination, myoclonus, shivering, or tremor.

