6. **Laboratory evaluation**. This will consist of a complete blood cell count with platelets and differential, a comprehensive metabolic panel (including electrolytes, renal function tests, liver function tests, glucose), and thyroid function tests. These tests will be drawn to rule-out any occult medical problems not detected by history and physical exam alone. A urine pregnancy test will be obtained from females of childbearing potential.

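### The only scheduled pregnancy test is at screening, so placebo patients who go on to open-label mirtazapine start it 10 weeks plus the screening interval after their last check

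*Combined protocol and SAP*

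**What the plan says.** All references are to section E of the combined protocol and SAP.

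- **Exclusion Criteria, item 5.** The heading is "Presence of any past or present medical conditions that would make treatment with mirtazapine unsafe". The conditions listed under it include "pregnancy (or being sexually active without using acceptable methods to prevent pregnancy").
- **Baseline Characterization, laboratory evaluation.** "A urine pregnancy test will be obtained from females of childbearing potential". No repeat is mentioned.
- **Schedule of Measures.** The row "Urine Pregnancy Test (females of child-bearing potential only") has a mark under SC. BL, W2, W4, W6 and W10 are blank.
- **Study Design.** "Participants will be seen at screen, baseline (randomization), and following 2, 4, 6, and 10 weeks of treatment". Screening and randomisation are thus separate visits, and no section sets a maximum time between them.
- **Safety Monitoring.** "A Comprehensive Metabolic Profile and CBC will be collected at baseline and endpoint". The laboratory work repeated at the end of the blinded phase therefore does not include a pregnancy test.
- **End of Trial Alternatives.** After the blind is broken at the end of the 10 weeks, placebo patients who remain clinically anxious "will be entered into a 10-week open-label trial of mirtazapine". The design is described as similar to the blinded phase, with outcome measures as the only stated difference. There is no schedule of visits or safety checks for this phase.

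**The concern.** The protocol itself judges pregnancy to be a reason not to give mirtazapine, and it provides a test to apply that judgement. A patient can first receive mirtazapine at two points: at randomisation, and at entry to the open-label phase after placebo. The schedule places the test at neither. At the second point the last scheduled result is more than two months old. A site that followed the schedule exactly could start an adolescent on mirtazapine without having confirmed, at that time, a condition on which the exclusion depends. What is at stake is patient safety and the soundness of the eligibility decision. Sample size, power, type I error and the efficacy analysis are not affected.

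**Working it through.** The plan gives no figure to reproduce. The check is a comparison of sections and a short timeline.

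**Inputs**
- Test time: screening visit only (Schedule of Measures).
- S: time from screening to baseline. Not stated, and not capped.
- Blinded treatment: 10 weeks (Study Design).
- Open-label start: after the 10-week phase is complete (End of Trial Alternatives).
- Planned allocation: 20 mirtazapine, 10 placebo (Sample Size Consideration and Power Analysis).

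**Gap between the test and first mirtazapine dose**
- Randomised to mirtazapine: gap = S.
- Randomised to placebo, then open-label: gap = S + 10 weeks at least, that is S + 70 days.

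The second result needs no assumption about S. It exceeds 10 weeks whenever screening comes before baseline.

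**Illustration of S (assumption, not needed for the conclusion).** Exclusion item 3 says of other antidepressants and benzodiazepines: "Subjects will need to be off medications from these classes for at least 5 elimination half-lives prior to randomization". This is a minimum with no maximum. The half-lives are not in the documents. Suppose they run from 1 to 7 days and a patient stops her drug only after screening. The minimum washout is then 5 × 1 = 5 days to 5 × 7 = 35 days. The open-label gap is at least 70 + 5 = 75 days (10.7 weeks) to 70 + 35 = 105 days (15 weeks).

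**How many patients.** The number of females of child-bearing potential is not given. As a rough guide only, the group's retrospective series (section C) had 5 females among 26. If that share applied here:
- all 30 patients: 30 × 5/26 = 5.8 females;
- placebo arm: 10 × 5/26 = 1.9 females.

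Both counts come before restriction to those of child-bearing potential within ages 5 to 17. The second also comes before restriction to those still anxious at week 10.

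**Sections side by side**

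| First possible mirtazapine dose | Pregnancy check stated at that point | Last scheduled check |
|---|---|---|
| Randomisation (BL) | None | Screening, S earlier |
| Open-label entry (after W10) | None | Screening, S + 10 weeks earlier |

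**The case against.** Several points on the other side are fair.

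*The exclusion and the schedule agree.* A reader might infer that item 5 and the schedule contradict each other in the blinded phase. They do not. Item 5 is an entry criterion that sets no recency for the test, and a test at screening serves it. What stands is that the schedule does not verify the criterion at the time of first dosing.

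*A similar design implies similar entry checks.* This is a reasonable reading of the open-label paragraph, since a pregnancy test is not an outcome measure. It also means one cannot say that the plan directs sites to rely on the old test; it is silent. But no section states a repeat, and the only schedule supplied puts the test at screening.

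*The washout may not widen the gap.* A reader might infer that the test always precedes a washout. Item 3 ties the washout to randomisation, not to screening, and it concerns only users of two drug classes. Some patients will already be off these drugs when screened. The interval is uncapped either way.

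*Other safeguards exist.* It would go too far to say that nothing could reveal a pregnancy. Adverse events and concomitant medication are recorded at every visit, the physician asks about doctor visits and other complaints, a physical examination is marked at W10, and item 5 excludes sexually active patients without acceptable contraception. These lower the risk. None of them is a test, and the protocol asks for a test as well as the contraception condition.

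*Few patients are concerned.* This is true. Quoting the whole placebo arm, 10 of 30, would overstate the group.

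**Conclusion.** The point holds as a gap in verification. The protocol's own safety exclusion for pregnancy is checked once, at screening. For placebo patients who move to open-label mirtazapine, that check is at least 10 weeks plus the screening interval old at first exposure. For patients randomised to mirtazapine it is as old as the screening interval, which the documents leave open. The first statement rests only on the marked schedule and the stated 10-week phase. It assumes that the open-label phase adds no check beyond those written down; if re-screening is intended, one sentence would settle the matter.

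The affected group is small, probably a handful at most if the sex ratio resembles the earlier series, and the documents give no count. The point concerns pregnancy status when mirtazapine is first given. It makes no claim about monitoring during treatment. It should be corrected, because the remedy is simple and the protocol itself calls the condition unsafe, but it does not threaten the trial's analysis.

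**What to change.** Reconcile four places: Exclusion Criteria item 5, the laboratory paragraph of Baseline Characterization, End of Trial Alternatives, and the Schedule of Measures. The aim is that the pregnancy check on which the exclusion relies is current at each point where mirtazapine can first be given, namely randomisation and open-label entry. The BL and W10 visits already take place and could carry the urine test the protocol already uses; the timing is for the sponsor to decide.

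Two clarifications belong with this. State the maximum interval from screening to baseline, or say that there is none and how the check is kept current. State which entry and safety checks apply to the open-label phase. The text should also use one label for the visit: the test is described under Baseline Characterization and the blood tests are said to be taken at baseline, while the schedule marks both at SC and leaves BL blank.

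The cost is a short edit, one or two extra urine tests for a small subgroup, and a sensitive conversation with some families. No analysis or sample size changes.
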